6.4 Sample Size and Power

Anticipating a participant retention proportion of 0.85, the estimated half-width of a 95% CI for the proportion based on 24 enrolled participants is 0.14, which would give a CI of (0.71,0.99). Assuming the overall proportion of sessions attended is 0.75 and an intra-participant correlation of 0.10, the estimated half-width of a 95% CI for the proportion out of a total of 96 possible participant-sessions is 0.10, which would give a CI of (0.65,0.85). Assuming a 15% dropout rate, a sample size of 20 across two groups at post-test is adequate to estimate the feasibility and to generate preliminary data for planning a larger trial.

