	(3) Intervention : Four weekly, 1 hour 30 minute group mindfulness training sessions co-facilitated by an experienced mindfulness instructor (Faculty advisor [name]) and a clinical psychologist with pain psychology training (PI [name]).					
	(4) Post-measures: Within 1-2 weeks after intervention, administered via online self-report questionnaires and with semistructured phone interview.					
Efficacy Evaluations	Feasibility and acceptability will be measured with 1) enrollment statistics, 2) study retention, 3) assessment completion, 4) session attendance, 4) home practice diaries, and 5) credibility questionnaire and semi-structured phone interviews assessing participant satisfaction. Secondary outcomes will be measured with self-report questionnaires.					

Pharmacokinetic Evaluations	N/A
Safety Evaluations	Participant self-report of adverse experiences in response to mindfulness meditation practice. Will assess during intervention sessions. Will monitor AEs/SAEs that may or may not be study related as reported by participants.
Statistical And Analytic Plan	Primary feasibility/acceptability outcomes will be analyzed using percentages and 95% CIs. The qualitative description method will be used for interview data by identifying major themes within the content and producing a descriptive summary of the data. Secondary outcomes will be analyzed using paired t-tests and by examining the pre/post intervention change in scores and their respective standard errors with 95% confidence intervals.
Data And Safety Monitoring Plan	The PI ([name]) is responsible for data quality management and ongoing assessment of participant safety. The faculty advisor ([name]) will advise PI [name] on issues of data quality management and assessment of safety.

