6.1 Primary Endpoint

The primary outcomes are feasibility and acceptability of the intervention and study procedures. Feasibility will be assessed as 1) ability to enroll 12 participants for one intervention group within 4-6 weeks, 2) participant retention, with a goal of 85% retention, 3) session attendance, with a goal of 75% sessions attended, 4) proportion of completed assessments and practice forms.

Acceptability will be assessed via credibility questionnaire and semi-structured interview assessing satisfaction with the intervention, barriers to engagement, and suggestions for improving the intervention or study procedures.

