6.3 Statistical Methods

Quantitative Analyses: Baseline demographic, pain medication use, and pain condition variables will be characterized using means and percentages and their standard deviations. Primary feasibility/acceptability outcomes will be analyzed using percentages (proportions) and 95% confidence intervals (CIs). Secondary outcomes will be analyzed by using paired t-tests and examining the pre/post intervention change in scores and their respective standard errors with 95% confidence intervals. Influence of the pretest score on change (i.e., ceiling and floor effects) will be investigated.

Qualitative Analyses: The qualitative description method will be used for interview data.²⁶ Major themes within the content will be identified and a codebook created. A test sample of interviews will be coded and the codebook refined, followed by coding remaining interviews. The outcome will be a descriptive summary of the contents of the data.

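### The planned 95% CI for retention, (0.71, 0.99), comes from the Wald formula, which covers about 89% at n = 24 and true retention 0.85; section 6.3 names no other method

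*Combined protocol and SAP*

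**What the plan says.** Section 6.1 makes retention one of the primary feasibility outcomes: "participant retention, with a goal of 85% retention". Section 6.4 rests the sample size on precision, not on a test. It begins "Anticipating a participant retention proportion of 0.85" and reports that "the estimated half-width of a 95% CI for the proportion" "based on 24 enrolled participants is 0.14, which would give a CI of (0.71,0.99").

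On the analysis itself, section 6.3 says "Primary feasibility/acceptability outcomes will be analyzed using percentages (proportions) and 95% confidence intervals (CIs"), and the synopsis says "Primary feasibility/acceptability outcomes will be analyzed using percentages and 95% CIs". Neither names a method for the interval, and no other section does.

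**The concern.** An interval that is symmetric about 0.85 and almost reaches 1 with only 24 people suggests the Wald formula. That formula is at its weakest when the sample is small and the proportion is near 1. Its real coverage can then fall well short of the label, and its limits can leave the range 0 to 1.

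Retention is a primary outcome, and a percentage with a 95% CI is its planned quantitative analysis. Section 6.4 also says the results are meant to inform a larger trial. For that use the lower limit matters most, because it shows how poor retention could plausibly be. If the only method on show sets that limit too high, later planning starts from an optimistic figure.

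**Working it through.** **Inputs.** n = 24 and anticipated retention 0.85 (6.4); goal 85% (6.1); two-sided 95%, z = 1.96 (6.4 gives the level; two-sided is assumed).

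**1. Reproduce the plan's figure.** Wald half-width = z·√(p(1−p)/n) = 1.96 × √(0.85 × 0.15/24) = 0.143. The interval is 0.85 ± 0.143 = (0.707, 0.993), which rounds to the stated (0.71, 0.99). The alternatives do not reproduce it: Wilson (0.66, 0.94), Clopper-Pearson (0.65, 0.96), Agresti-Coull (0.65, 0.95), Jeffreys (0.67, 0.95), a t quantile with 23 df (half-width 0.151), or a continuity correction (half-width 0.164).

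**2. Exact coverage at true retention 0.85.** Let X ~ Binomial(24, 0.85). Coverage is the total probability of the counts whose interval contains 0.85.

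- Wald contains 0.85 for X = 16 to 22 only.
- It lies wholly above 0.85 at X = 23 (probability 0.0857) and X = 24 (0.0202), together 0.106.
- It lies wholly below 0.85 at X ≤ 15, probability 0.006.
- The miss rate is 0.112, so coverage is 0.888.
- Wilson misses at X = 24 (0.0202) and X ≤ 16 (0.0199), so its coverage is 0.960. Clopper-Pearson also gives 0.960.

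**3. Other true values.** Coverage is uneven because counts are discrete.

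| True retention | Wald coverage |
|---|---|
| 0.80 | 87.3% |
| 0.82 | 92.7% |
| 0.85 | 88.8% |
| 0.86 | 85.5% |
| 0.88 | 94.8% |
| 0.90 | 91.3% |
| 0.95 | 70.7% |

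Over a fine grid from 0.75 to 0.95:

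| Method | Mean coverage | Lowest |
|---|---|---|
| Wald | 88.6% | 70.7% (at 0.95) |
| Wilson | 95.6% | 92.4% (near 0.851) |
| Clopper-Pearson | 97.9% | above 95% |

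**4. Intervals at the counts that meet the goal.** 0.85 × 24 = 20.4, so an observed 85% needs at least 21 retained (20/24 is 83.3%).

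| Retained | Wald | Wilson | Clopper-Pearson |
|---|---|---|---|
| 21/24 | (0.743, 1.007) | (0.690, 0.957) | (0.676, 0.973) |
| 22/24 | (0.806, 1.027) | (0.742, 0.977) | (0.730, 0.990) |
| 23/24 | (0.878, 1.038) | (0.798, 0.993) | (0.789, 0.999) |
| 24/24 | (1.000, 1.000) | (0.862, 1.000) | (0.858, 1.000) |

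At true retention 0.85, P(X ≥ 21) = 0.505: 0.485 for 21 to 23, where the Wald upper limit passes 1, and 0.020 for 24, where its width is zero.

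**5. The planning interval by better methods, at 0.85.** For Wilson, z²/n = 3.84/24 = 0.160. The centre is (0.85 + 0.080)/1.160 = 0.802. The half-width is (1.96/1.160) × √(0.85 × 0.15/24 + 3.84/(4 × 24²)) = 0.141, giving (0.661, 0.943). Clopper-Pearson, evaluated at the non-integer count 20.4, gives (0.646, 0.961), half-width 0.158.

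**The case against.** The best defence is that section 6.4 is a planning statement. It shows what precision 24 people give, and that message survives: the half-width is 0.14 by Wald and 0.14 by Wilson. A simple planning formula does not bind the analyst, and 6.3 leaves the method open, so impossible limits arise only if Wald is carried into the analysis. The 85% goal is set on the observed proportion, not on a confidence limit, and any reader given the count can compute another interval. All of this stands, and it bounds the harm.

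A second objection is that coverage belongs to a procedure at a given true value, not to the single interval (0.71, 0.99), and that it moves with that value. Wald reaches 94.8% at 0.88, while Wilson drops from 96.0% at 0.85 to 92.4% at 0.851, so the seven-point gap at exactly 0.85 overstates the local contrast. That is fair. But the average over 0.75 to 0.95 still favours Wilson by seven points (95.6% against 88.6%), and Wald also falls well below its value at 0.85, for example to 81.4% at 0.875.

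A third is that the replacement planning intervals use 20.4 retained, which cannot occur. That is true, and it applies equally to the plan's own figure. At whole counts Wilson gives (0.64, 0.93) for 20/24 and (0.69, 0.96) for 21/24.

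None of these points supports the stated lower limit of 0.71.

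**Conclusion.** The concern holds. The interval in 6.4 is correctly calculated from a method that does not deliver its nominal level here: 88.8% at the plan's own 0.85 and n = 24, and 88.6% on average over true retention of 0.75 to 0.95. The error is in the favourable direction. The stated lower limit is about five points too high (0.71 against 0.66 by Wilson or 0.65 by Clopper-Pearson), and the upper limit is three to five points too high (0.99 against 0.94 or 0.96).

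This rests on 24 independent participants with a common retention probability and a two-sided 95% level. Whether Wald would be used in the final analysis is not certain; it is the only method the documents show. The consequence is a misstated error bar on a primary outcome, not a wrong sample size or a wrong feasibility decision. It should be corrected before the data are seen, because there is about an even chance of a result at which the formula fails visibly and a method would have to be picked afterwards.

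**What to change.** - **Section 6.3 (and the synopsis, if it is to match):** name a Wilson 95% interval for the retention proportion, or Clopper-Pearson if guaranteed coverage is preferred.
- **Section 6.4:** restate the planning interval as about (0.66, 0.94) for Wilson, or (0.65, 0.96) for Clopper-Pearson.
- **Section 6.1 (optional clarification):** note that an observed 85% of 24 means at least 21 retained.

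Keep 24 participants and the 85% goal. The cost is one phrase and one interval. The half-width stays at 0.14 with Wilson and becomes 0.16 with Clopper-Pearson, and the quoted lower limit becomes about five points less favourable. The change concerns retention only. Session attendance is repeated within participants, as 6.4 recognises with its intra-participant correlation, so a plain binomial interval should not be carried over to it.

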6.5 Interim Analysis

We are not planning any pre-specified interim analyses for any reason. The study may be suspended by the PI if a serious adverse event occurs that is deemed to be secondary to our intervention. We do not expect any serious adverse events given the low risk of this study.

7 STUDY INTERVENTION (drug, device or other intervention details)

The mindfulness intervention will consist of four, weekly group mindfulness skills sessions each lasting 1 hour and 30 minutes. Each session will have approximately 85 minutes of intervention material scheduled, with time for a 5-minute break in the middle. Sessions will be co-instructed by PI [name] and faculty advisor [name]. All sessions will take place at the same UNC clinic or conference room location on a weekday or week-night. Participants will receive guided audio recordings for mindfulness skills practice, in addition to a binder with course handouts. Participants will be asked to practice for up to 30 minutes daily and to log their practice in the home practice questionnaires that will be emailed and completed using REDCap surveys. Home practice questionnaires will ask about which mindfulness skills were practiced and the number of minutes practiced. Participants will be asked to attend all four sessions as is possible and session attendance data will be collected and evaluated.

Mindfulness skills taught will include sitting meditation with mindfulness of breath, thoughts, emotions, or physical sensations; body scan meditation; walking meditation; and mindfulness of routine daily activities. Mindfulness training involves the intentional self-regulation of attention towards a specific aspect of present-moment experience (e.g. the breath, physical sensations, thoughts, emotions, sounds) while noticing and releasing cognitive fixation on thoughts and emotions about the past or future, or judgments and resistance towards present-moment experience. Didactic content will be presented and discussed amongst the group, with content focusing on topics such as defining mindfulness and how it can help with stress and pain management, the difference between mindfulness and being on autopilot, stress and its relationship to chronic pain, how our perceptions affect stress, the relationship between pain and distressing thoughts and emotions, acceptance of pain and unwanted experiences, using mindfulness in daily life. See **Appendix B** for session-by-session content and home practice assignments.

8 STUDY INTERVENTION ADMINISTRATION(if applicable)

Not applicable – this is a single-group study, so participants will not be randomized, and it is not possible to blind to intervention condition.

9 SAFETY MANAGEMENT

Adverse Event/Serious Adverse event monitoring procedures: Participant safety will be monitored through contact with the intervention instructors (PI and faculty advisor) and

RA. If study staff should learn of any safety issues or injuries among study participants, the appropriate information will be gathered by the PI, including the date of event/injury, the nature/description of the event or injury, and any treatment received as a result of the event or injury. This information will be recorded in adverse event monitoring forms (see Appendix D). We anticipate based on previous research of mindfulness training interventions that the study will pose minimal safety risk; however, AEs/SAEs will be assessed by PI [name], faculty advisor [name], and Co-I [name] as to the likelihood that the event is study-related and appropriate action taken if necessary (e.g. participant withdrawal from study). In addition, participants will have opportunities to report any unwanted experiences related to practice of mindfulness skills or participation in the group sessions (e.g. emotional or physical discomfort or distress) during intervention sessions, home practice questionnaires, post-intervention interview, and by contacting the study staff between sessions. Participants will be made aware that they can contact study staff to discuss any discomfort they experience as a result of the intervention at any time.

Adverse Event/Serious Adverse Event reporting procedures: All AEs/SAEs will be monitored by the PI, who will gather all safety-related information from participants, record the event in the monitoring form, and report events as soon as possible (same day or next business day) to the UNC IRB.

Medical Emergency Procedures: Participants will be informed in the consent form and upon enrolling in the study that they should call 911 or go to their nearest emergency department should they experience a medical or psychiatric emergency during the time of their study participation. Should a medical emergency occur during a study intervention session, the emergency department will be contacted immediately.

10 DATA COLLECTION AND MANAGMENT

All participant self-report questionnaires will be completed through secured data collection programs (REDCap). Every participant will have a unique identifier and will receive unique survey links connected with their identifier. After data collection, raw survey responses will be converted into the required file types for analysis. Case report forms (see **Appendix D**) will be used to monitor safety and to record feasibility data, such as eligibility, attendance, assessment completion, and study withdrawal. All case report forms, survey responses, and data files will be stored on UNC's secure network, and will be accessible by approved study staff only in a secured network folder. Participant identifying information (name, birth date) will be kept in a separate secured file on UNCs secure server, linking each participant to their unique study identifier, and will not be linked to any study data. This file will only be accessible by the PI and any approved study staff. All study staff will have completed a required training course in

the protection of human subjects before interacting with research participants or with study-related files or data.

11 RECRUITMENT STRATEGY

We will recruit via pain management providers within UNC clinics and by UNC email advertising. Providers and clinic staff in UNC clinics that assist with pain management will be informed of the study, given a brief written description of the study, and given written information (flyers) to provide to patients that includes study information and contact information. Providers may also ask patients for verbal permission to give the study investigator their name and contact information so study personnel can contact them directly about the study. Clinics will include but not necessarily be limited to the Department of Anesthesiology Pain Clinic, the Spine Center, Physical Medicine and Rehabilitation, and Internal Medicine.

12 CONSENT PROCESS

Individuals will complete phone screening with the PI or RA. Participants will be given information about the nature of the phone screening and asked if they give permission to continue with the phone screen. If an individual is eligible for the study, the screener will review the information provided in the consent form with the individual over the phone, including the purpose of the research, the nature of involvement, the estimated risk of involvement, the potential benefits of participation, the right to stop participation at any time, and who to contact with questions about the research or consent process. The individual will have the opportunity to ask any questions over the phone. They will then be sent an email with the link to the online consent form, asked to read the consent form, and if they agree to participate, to sign the online consent form. Participants will have the opportunity to contact study staff to ask additional questions after reading the online consent form and before signing it.

13 PLANS FOR PUBLICATION

A manuscript reporting the results of this study with regards to feasibility, acceptability, and preliminary effects of the intervention will be submitted for publication in a peer-reviewed journal that has interest in nonpharmacological interventions and/or mindfulness-based interventions for chronic pain management. The results may also be disseminated at a conference (e.g. American Pain Society, Integrative Medicine and Health), and results will be used to provide preliminary data for future grant proposals.

APPENDIX A.
Schedule of Evaluations

Assessment	Phone Screening	Consent: Online form	Pre-test: Online Survey	Treatment Visit 1 (Week 1)	Treatment Visit 2 (Week 2)	Treatment Visit 3 (Week 3)	Treatment Visit 4 (Week 4)	Post-test: Online Survey	Post-test: Phone Interview
Inclusion/Exclusion Criteria	Х								
Informed Consent Review and Form	х	Х							
Feasibility: Enrollment, retention, attendance, data collection	х	Х	х	х	х	х	х	х	х
Acceptability: Satisfaction, barriers, suggestions to improve intervention								х	х
Demographics, pain conditions/regions			Х						
Instructor fidelity to intervention protocol				х	Х	х	Х		
Daily home practice and pain intensity/interference (exploratory outcomes)				х	X (daily from W1- 2)	X (daily from W2- 3)	X (daily from W3- 4)		
Pain medication usage			Х					Х	
Secondary outcomes: PROMIS outcomes, psychological variables			х					х	
Credibility Questionnaire					Х				
Adverse Reactions/Events				х	Х	Х	Х		

Appendix B. Measures

Scale or Item	Description
Screening Measures/Items	
Drug Abuse Screening Test ²⁷ (DAST)-10	10 items; assess drug use in the past 12 months
Alcohol Use Disorders Identification Test	3 items; assesses alcohol consumption, drinking
(AUDIT) ^{28,29}	behaviors, and alcohol-related problems
Chronic pain	Have you experienced pain on a daily basis for at least
	3 months?
Pain bothersomeness	How bothersome was your pain in the previous week?
	(rating scale 0-10).
Pain interference with general activities	How much did your pain interfere with your general
	activities in the past week? (rating scale 0-10).
Diagnosis of mental illness with psychotic	Have you ever been diagnosed with schizophrenia,
features	schizoaffective disorder, or another psychiatric
	disorder with psychotic symptoms?
Psychiatric hospitalization in past 2 years	Have you ever been hospitalized for mental health
	reasons? When was the last hospitalization?
Previous mindfulness training	Have you ever participated in mindfulness training or
	course? Have you ever had a regular mindfulness
	practice? When?
Baseline-only Measures	
Demographic variables	Age, race/ethnicity, education, income, marital status
Pain conditions and regions	e.g. fibromyalgia, osteoarthritis, low-back pain,
	migraine, neck pain, etc
Baseline and Post-test Measures*	
Pain Medication Use	Pain medications taking, frequency, and dose
Physical Function (short-form 4a) ³⁰	4 items; difficulty with activities of daily living
Anxiety (sf 4a)	4 items; suggestive of anxiety in the past 7 days
Depression (sf 4a)	4 items; suggestive of depressed mood in past 7 days
Sleep Disturbance (sf 4a)	4 items; sleep quality and disturbance in past 7 days
Pain Interference (sf 6b)	6 items; degree to which pain interferes with life
Pain Intensity	1 item; average pain intensity past 7 days (0-10)
Positive Affect and Wellbeing	9 items;
Perceived Stress Scale – 4	4 items; global measure of perceived stress
Pain Catastrophizing Scale ³¹	13 items; 3 subscales characterizing thoughts and
	feelings when in pain – rumination, magnification,
	helplessness
Chronic Pain Acceptance Questionnaire ³²	20 items; acceptance of experiencing pain
Freiberg Mindfulness Inventory	14 items; measures all aspects of mindfulness
Intervention Satisfaction	1 likert-type item asking how satisfied are with the
2.22	intervention oveall
Credibility Questionnaire ^{34,35} (after session	5 items assessing opinions about the intervention
2)	including how logical it seems, confidence, likelihood
	of recommending it, importance, and success

^{*}Italicized items are PROMIS Measures

Appendix C. Case Report Forms

Phone-Screening

Screen ID	Date	Eligible (Y/N)	Reason Ineligible

Subject Status

Participant ID	Date Enrolled	Group (1,2)	Date Completed Study	Study Status	Reason for Withdrawal	Baseline Assessment (Date) Incentive?	Post-Intervention Assessment (Date) Incentive?	Post-Intervention Phone Interview (Date) Incentive?

Status:

A = Active W = Withdrew
C = Completed L = Lost to follow-up

Session Attendance

Pt. ID	Session 1 (Y/N)	Session 2 (Y/N)	Session 3 (Y/N)	Session 4 (Y/N)	Notes (reasons missed)

Pt. ID	AE Onset	AE End	Severity	SAE? (Y/N)	Relatedness	Action Taken	Outcome	Comments

Adverse Events

Severity of AE: Relatedness to Intervention: 1 = Mild 0 = Definitely unrelated

2 = Moderate 1 = Unlikely 3 = Severe 2 = Possibly related 4 = Life threatening or disabling 3 = Probably related

4 = Definitely related
